5.5 Population and indications

5.5.1 Indication for use Ponto implant and Ponto system

The Ponto system is intended for the following patients and indications:

- Patients with conductive or mixed hearing losses, who can still benefit from amplification of the sound. The pure tone average (PTA) bone conduction (BC) threshold (measured at 0.5, 1, 2 and 3 kHz) of the indicated ear should be better than or equal to 45 dB HL for use with the Ponto Plus, Ponto 3 and Ponto 4 sound processors, 55 dB HL for use with the Ponto Pro Power, Ponto Plus Power and Ponto 3 Power sound processors and 65 dB HL for use with the Ponto 3 SuperPower and Ponto 5 65 sound processors.
- Bilateral fitting is applicable for most patients having a symmetrically conductive or mixed hearing loss. The difference between the left and right sides' BC thresholds should be less than 10 dB on average measured at 0.5, 1, 2 and 4 kHz, or less than 15 dB at individual frequencies.
- Patients who have a profound sensorineural hearing loss in one ear and normal hearing in the opposite ear (i.e. single sided deafness or "SSD"). The pure tone average (PTA) air conduction (AC) threshold of the hearing ear should then be better than or equal to 20 dB HL (measured at 0.5, 1, 2 and 3 kHz).
- Also indicated for any patient who is indicated for an air-conduction contralateral routing of signals (AC CROS) hearing aid, but who for some reason cannot or will not use an AC CROS.

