9.4 Subject population

Patients considered for inclusion into this clinical investigation will be found among those who have already received audiological and otological evaluation and are found to be suitable candidates for BAHS treatment.

9.4.1 *Inclusion criteria*

1. 18 years of age or older
2. Patient indicated for surgical intervention with a bone anchored hearing system
3. Signed informed consent
4. Adequate bone quality to allow for a Ponto implant insertion, as judged by the investigator, and an expected bone thickness above 5 mm, where no complications during surgery are expected
5. Skin thickness of 12 mm or less at the implant site

9.4.2 *Exclusion criteria*

Subjects meeting any of the following criteria will not be permitted to participate in the investigation:

1. Patient undergoing re-implantation
2. Patient who are unable or unwilling to follow investigational procedures/requirements, e.g. to complete quality of life scales
3. Known condition or previous treatment that could jeopardize skin condition and wound healing over time as judged by the investigator (e.g. uncontrolled diabetes, previous radiotherapy in the area of interest)
4. Known medical condition that contraindicate surgery as judged by the investigator
5. Known and/or planned pregnancy at time of surgery
6. Any other known condition that the investigator determines could interfere with compliance or investigation assessments
7. Simultaneous participation in another clinical investigation with pharmaceutical and/or medical device which might cause interference with investigation participation

9.4.2.1 *Relationship of investigation population to target population*

The investigation population correlates very well to the target population of the investigational device (see section 5.5). Adult patients with all types of indicated hearing losses, whether uni- or bilateral fitted, are potentially eligible for inclusion. Patient participation is completely voluntary. Patient groups not included in the investigation relates to diseases or conditions that may compromise skin conditions, pregnancy, cognitive impairment or any other known condition that could interfere with compliance of the investigation. These patient groups may be treated outside of the study if judged suitable by the treating physician.

9.4.3 *Number of Subjects*

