A total of 50 patients will be included in the investigation. All potential subjects are already planned for treatment with a percutaneous bone-anchored hearing device and will be consecutively included in the investigation using the inclusion and exclusion criteria stated above. Bilateral surgeries are allowed. Bilaterally operated patients will account as one patient out of the 50, whereas both implant/abutment complexes will be accounted for in the implant-level analyses. The investigation will be performed at seven different sites with a maximum of 15 and an intended minimum of three subjects per site.

CONFIDENTIAL

The investigation will be performed at the following sites:

1. Guy's and St Thomas' Hospitals, London, UK
2. Addenbroke's Hospital, Cambridge, UK
3. Queen Elizabeth Hospital, Birmingham, UK
4. Sahlgrenska University Hospital, Gothenburg, Sweden
5. Aalborg University Hospital, Aalborg, Denmark
6. Odense University Hospital, Odense, Denmark
7. Radboud University Medical Center, Nijmegen, The Netherlands

Subject inclusion is estimated to start in the last quarter of 2020, depending on when approvals from concerned ethical committees are granted. The recruitment period will be ongoing until the total number of subjects has been reached and is estimated to last for approximately 6 months. The end of the investigation is therefore expected to be around the end of the second quarter in 2022, i.e. a total study duration of 1.5 year. Since the primary endpoint is due at the 3-month visit, corresponding data will be extracted, analysed and reported as applicable, with an approximate start in the end of the third quarter in 2021. The total duration of the investigation for each subject is 12 months (from implant installation date).

Expected time schedule for investigation milestones

Start of enrolment:	Q4 2020
End of enrolment:	Q2 2021
Primary endpoint:	Q3 2021
End of study:	Q2 2022

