10.3 Clinical investigation assessments

10.3.1 *Implant/abutment complex capability to provide a reliable anchorage for a sound processor after MONO surgical procedure*

The primary endpoint variable of this study ('capability to provide a reliable anchorage for a sound processor') is a composite variable depending on the outcome of five other variables:

- I. Implant in situ [Implant survival: No/Yes] (see section 10.3.2);
- II. Implant stable [Implant stability: No/Yes] (see section 10.3.3);
- III. Absence of:
 - a. adverse skin reaction (Holgers score ≥ 2) preventing use of sound processor [No/Yes] (see section 10.3.4.2);
 - b. pain preventing use of sound processor on implant/abutment complex [No/Yes] (see section 10.3.6);
 - c. skin overgrowth preventing use of sound processor on the implant/abutment complex [No/Yes] (see section 10.3.4.3)

For this composite endpoint to result in a positive outcome [=Yes], all involved variables need to be answered with [Yes]. If any involved variable is answered with [No], the outcome of the composite variable will be considered a failure [=No]. The rate of subjects (or implant/abutments complexes, if a subject is treated bilaterally) with a positive outcome will be used to calculate point estimates of the proportions with a two-sided 95% confidence interval. These point estimates and corresponding confidence intervals will be used to establish the expected level of implant/abutment complexes that are capable to provide a reliable anchorage (i.e. usage) for a sound processor, at the respective time point.

10.3.2 *Implant survival*

At each follow-up visit, the Investigator will assess whether the implant is still in situ (in place) by means of a [No/Yes] question. The rate of implant survival will be calculated from the number of

implants in situ over the number of implants that were placed. The rate of implant failure will be implicit. The reason for any failure (e.g. spontaneous, trauma etc.) will be documented.

10.3.3 *Implant stability*

Implant stability will be assessed by means of the subjective clinical judgement of the investigator. If the implant is firmly situated in the bone and assumed to be sufficiently osseointegrated when gently manipulating the implant/abutment using the fingers, it is judged stable [Yes]. If the implant is loose, with a lack of osseointegration, the implant is judged not stable [No].

10.3.4 *Skin assessments*

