12.2 Sample size

The sample size in the investigation is not hypothesis-driven, but rather based on:

1. The typical size of prospective studies on surgical outcomes within the bone-anchored hearing system field.
2. The precision of the primary endpoint. The precision can be expressed as the width of the two-sided 95% confidence interval (CI).

Prospective studies from recent years were identified through literature search as part of the clinical evaluation. One study was excluded (Dumon *et al.* 2016) since it covered a period of 12 years, which cannot be considered as typical. The identified studies (Table 6) included a median of 25 patients and an average of 35 patients. For larger comparative studies the group size varied from 21 to 39 patients.

Table 6. Prospective BAHS-studies published between July 2016 and June 2019

Year	Title	Author	Implant Test (N)	Implant Control (N)	Adult (N)
2018	Minimally Invasive Ponto Surgery Versus the Linear Incision Technique With Soft Tissue Preservation for Bone Conduction Hearing Implants: A Multicenter Randomized Controlled Trial.	Calon et al.	33	30	63
2019	Three-Year Clinical and Audiological Outcomes of Percutaneous Implants for Bone Conduction Devices: Comparison Between Tissue Preservation Technique and Tissue Reduction Technique.	Kruyt et al.	25		25
2017	Bone Anchored Hearing Implant Surgery: 1 Year Follow-Up Data Shows No Effect of Hydroxyapatite Coating on Soft Tissue Reaction after Loading at 1 Week.	Høgsbro et al.	25		25
2018	Three-year Outcomes of a Randomized Controlled Trial Comparing a 4.5-mm-Wide to a 3.75-mm-Wide Titanium Implant for Bone Conduction Hearing.	Kruyt et al.	39	21	57
2018	The clinical outcome and microbiological profile of bone-anchored hearing systems (BAHS) with different abutment topographies: a prospective pilot study.	Trobos et al.	5	7	12
2018	Wide diameter bone-anchored hearing system implants: a comparison of long-term follow-up data between tissue reduction and tissue preservation techniques.	Reznitsky et al.	24	24	48
2017	Baha implant as a hearing solution for single-sided deafness after retrosigmoid approach for the vestibular schwannoma: surgical results.	Boucek et al.	5	11	16

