The primary endpoint of this investigation is the ‘capability of implant/abutment complex to provide a reliable anchorage for the sound processor at three months after MONO surgical procedure’. The primary endpoint will be presented by a point estimate (of the proportion) combined with a two-sided 95% CI, to reflect the level of successful implant/abutment complex installations using the MONO surgical procedure. Assuming a ‘success rate’ of 85% (conservative approach) three months after surgery, and with a confidence interval width of 20% points, the sample size needed is 50 patients. With a proportion of loadable implant/abutment complexes at three months of 95%, the resulting CI would be 11%.

Based on the above, the sample size was decided to be 50 patients.

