12.3 Statistical methods and analytical procedures

Descriptive statistics will be used. The primary endpoint will be presented both as number and percentage, and by point estimates of the proportions combined with a two-sided 95% CI.

For secondary endpoints, the distribution of categorical and dichotomous variables will be presented both as number and percentage, although the composite variable will be presented as for the primary endpoint. Data will be presented for each time separately as well as across visits, where applicable. The distribution of continuous variables will be given as Mean, standard deviation (SD), Median, Minimum and Maximum.

For the safety endpoint, device deficiencies, adverse events and serious adverse events related to the device will be descriptively reported using frequency tables and listings.

All statistical analyses are to be explained in detail in a statistical analysis plan (SAP). Any deviations from the original analysis plan will be described in a CIP amendment, as deemed appropriate.

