12.4 Missing data and special considerations

Missing data will not be imputed. For the primary endpoint, subjects withdrawn from the study due to loss of implant placed during the study (extrusion or elective removal) will be included in the analysis as a treatment failure (i.e. implant/abutment complex not in situ).

In case of any bilaterally implanted patient, implants will be handled as independent from each other for all implant-related variables, since this is considered more clinically relevant. Patient-variables such as patient characteristics and questionnaires will be presented on a patient-level.

No bias nor confounding factors are expected due to the single-arm design.

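### Treating a bilateral patient's two implants as independent makes the composite's 95% CI too narrow whenever bilateral patients are enrolled and their outcomes are positively correlated

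*Combined protocol and SAP*

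**What the plan says.** Section 12.4 sets the rule: "In case of any bilaterally implanted patient, implants will be handled as independent from each other for all implant-related variables". The only reason it gives is clinical relevance.

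The composite is covered by this rule. Section 10.3.1 says of the composite: "The rate of subjects (or implant/abutments complexes, if a subject is treated bilaterally) with a positive outcome will be used to calculate point estimates", with a two-sided 95% CI. Section 9.4.3 counts a bilateral patient once towards the 50, yet "both implant/abutment complexes will be accounted for in the implant-level analyses". With b bilateral patients the denominator is therefore 50 + b implants.

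Section 12.2 states the primary result as an estimate with an interval: "The primary endpoint will be presented by a point estimate (of the proportion) combined with a two-sided 95% CI". Section 8.2 repeats the composite at 6 and 12 months, and section 12.3 gives it the same presentation there: "although the composite variable will be presented as for the primary endpoint".

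Bilateral patients are expected in principle. Section 9.4.2.1 says "Adult patients with all types of indicated hearing losses, whether uni- or bilateral fitted, are potentially eligible for inclusion", section 9.3 provides extra kits for bilateral surgery, and no cap is set. The text contains no clustered variance and no patient-level sensitivity analysis. It does not name the interval method, and section 12.3 leaves analysis detail to the SAP.

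**The concern.** Two implants in one person share that person's skin, healing capacity, comorbidity and way of reporting pain, and the composite includes skin reaction, pain and skin overgrowth. The plan itself treats patient-level factors as relevant: exclusion criterion 3 concerns conditions that could impair skin and wound healing, and section 10.1 records diabetes, skin disease, smoking and steroid use. Positive correlation is therefore plausible, although the documents do not quantify it.

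Counting such implants as independent credits the study with more information than it has. The study has no comparator and no hypothesis test. The estimate and its CI are the stated result, so a CI that is too narrow misstates that result directly.

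**Working it through.** **The plan's own figure.** Section 12.2 gives 50 patients for a 20-point CI at 85% success. The Wald formula gives n = (2 × 1.96 / 0.20)² × 0.85 × 0.15 = 48.98, so 49. At n = 50 the width is 2 × 1.96 × √(0.1275/50) = 19.8 points. At 95% success the Wald width is 12.1 points, or 11.0 if the upper limit is cut at 100%, which matches the stated 11%. The planned size is reproduced, with no allowance for pairing.

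**Design effect.** Let b of 50 patients be bilateral, n = 50 + b implants, p the success rate and ICC the within-patient correlation. Each pair adds a covariance term 2 × ICC × p(1−p) to the variance of the total, so

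Var(p̂) = [p(1−p)/n] × DE, with DE = 1 + (2b/n) × ICC.

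DE exceeds 1 for any b ≥ 1 and ICC > 0. The standard error is understated by 1 − 1/√DE.

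**Inputs.** The 50 patients and 85% come from section 12.2. Both b and ICC are assumptions. Example with b = 10 and ICC 0.5: n = 60, DE = 1 + (20/60) × 0.5 = 1.167, √DE = 1.080. The naive Wald width is 2 × 1.96 × √(0.1275/60) = 18.1 points, and the correct width is 18.1 × 1.080 = 19.5.

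Results at ICC 0.5 (1.0 in brackets):

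| b | n | DE | SE understated | Naive Wald width | Correct Wald width |
|---|---|---|---|---|---|
| 1 | 51 | 1.020 (1.039) | 1.0% (1.9%) | 19.6 | 19.8 (20.0) |
| 3 | 53 | 1.057 (1.113) | 2.7% (5.2%) | 19.2 | 19.8 (20.3) |
| 5 | 55 | 1.091 (1.182) | 4.3% (8.0%) | 18.9 | 19.7 (20.5) |
| 10 | 60 | 1.167 (1.333) | 7.4% (13.4%) | 18.1 | 19.5 (20.9) |
| 20 | 70 | 1.286 (1.571) | 11.8% (20.2%) | 16.7 | 19.0 (21.0) |

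At ICC 0.2 the understatement is 1.1% with 3 and 3.2% with 10. At ICC 0.5 it first reaches 5% at b = 7 and 10% at b = 16. The largest correct width over all b and all ICC from 0 to 1 is 21.0 points (b = 17, ICC 1).

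**Exact coverage of the naive interval.** Pair outcomes have P(both succeed) = ICC × p + (1−ICC) × p² and P(both fail) = ICC × (1−p) + (1−ICC) × (1−p)². These are convolved with a Binomial(50−b, p) for the unilateral patients. With b = 10:

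| Interval | 85% success, ICC 0 / 0.5 / 1 | Mean over 80–95% success, ICC 0 / 0.5 / 1 |
|---|---|---|
| Wald | 94.4 / 92.4 / 90.2% | 91.7 / 89.4 / 87.1% |
| Wilson | 95.6 / 93.8 / 91.9% | 95.2 / 93.4 / 91.6% |
| Clopper-Pearson | 97.2 / 95.7 / 94.2% | 96.9 / 95.5 / 94.0% |

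With b = 3 at 85%, Wilson and Clopper-Pearson both give 96.8 / 96.4 / 95.9%. Wald is already at 90.6% with zero correlation, so its shortfall there is mostly not due to pairing. Averaged over 80–95% success, Wilson gives 95.3 / 94.8 / 94.2% with 3 bilateral patients, and 92.0% (88.6%) at ICC 0.5 (1.0) with 20. At 95% success with b = 10, Wilson still covers 95.9% (94.9%).

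**How many bilateral patients?** The plan makes no forecast; the only hint is Table 6. Its implants sum to 63+25+25+60+12+48+16 = 249 and its adults to 63+25+25+57+12+48+16 = 246. The adult column is the plan's patient count: 246/7 = 35.1 and its median is 25, matching "The identified studies (Table 6) included a median of 25 patients and an average of 35 patients". Six studies list equal numbers; one lists 60 implants in 57 adults, unexplained. If those 3 extra implants are second sides, that study's rate gives 3/57 × 50 = 2.6 bilateral patients in 50. Pooling all seven gives 3/246 × 50 = 0.6.

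**The case against.** The strongest reply is that the effect may be negligible here. Pooled Table 6 suggests fewer than one bilateral patient in 50. With one, the standard error is understated by 1.0% (1.9%) and Wilson coverage at 85% moves only from 95.3% to 95.0% (94.8%). Nothing in the documents supports 10 or 20 bilateral patients, or a correlation as high as 0.5. With 3 at 85% success, the clustered interval proposed below has the same coverage as the naive Wilson to one decimal, and costs some width. The unnamed interval matters more than pairing: with 10 bilateral patients, mean coverage at zero correlation already ranges from 91.7% (Wald) to 96.9% (Clopper-Pearson). The analysis is descriptive, and pairing does not bias the point estimate.

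All of this is true, and it limits the importance of the point. It does not rescue the rule. The direction of the error is certain once b ≥ 1 and ICC > 0. The plan does not cap bilateral enrolment and says in section 5.5.1: "Bilateral fitting is applicable for most patients having a symmetrically conductive or mixed hearing loss". Table 6 is weak evidence for a low number, since it does not report bilateral patients as such. Independence is also an explicit instruction, not a detail left open for the SAP.

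**Conclusion.** The concern holds, conditionally. If any bilateral patients are enrolled and their two outcomes are positively correlated, the composite's 95% CI at 3, 6 and 12 months is narrower than the data support. With none enrolled, or zero correlation, the rule does no harm.

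The size depends on two quantities that the documents do not give. It is small at the roughly 1 to 3 bilateral patients that Table 6 weakly suggests, moderate at 10, and material at 20. The 20-point precision target is not seriously threatened, and no formal decision turns on the interval. The correction should be made because the CI is the study's stated result and correcting it costs almost nothing, but it does not put the study in doubt.

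**What to change.** In section 12.4 and the SAP, keep the per-implant proportion but name the interval and compute it with the patient as the cluster at 3, 6 and 12 months. A workable choice is a Wilson interval on the Rao-Scott effective sample size n/DE. Estimate DE as the cluster-robust variance (factor 50/49) over p̂(1−p̂)/n, floor it at 1, and set it to 1 when all implants succeed or all fail. Report the number of bilateral patients beside the CI.

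No new data are needed: section 13 already stores left and right entries under one subject number. The cost is a slightly wider interval. At 85% success, mean Wilson width changes as follows:

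| b | ICC 0 | ICC 0.5 |
|---|---|---|
| 3 | 18.9 to 19.1 | 18.8 to 19.5 |
| 10 | 17.8 to 18.1 | 17.7 to 19.2 |

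At ICC 0.5 (1.0) and 85% success, the proposed interval covers 94.8% (94.5%) with 10 bilateral patients and 94.9% (95.0%) with 20. Averaged over 80–95% success with 20, it covers 94.6% (93.9%).

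Its limit is sparse data. At 95% success with 10 bilateral patients and ICC 0.5, the floor or the boundary rule returns the naive interval in 22% of trials, although coverage there is 96.5%.

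A minor related point: sections 9.4.4 and 12.4 should be reconciled on whether a bilateral patient's remaining implant is still followed after the other is lost.

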12.5 Timing of analysis

Results will be compiled and reported when all subjects have reached the primary endpoint of the study, i.e. after three months. End-of-study data will be compiled after 12 months. No other interim analysis is planned for.

13 DATA MANAGEMENT

All personal data collected and processed concerning the subjects participating in the investigation are protected under the Regulation (EU) 2016/679 (GDPR) and will be handled accordingly. Further, professional secrecy regarding subject information and data applies to all involved personnel, including sponsor representatives.

Names and/or other explicit personal identification information will not be collected or recorded for investigational purposes, with one crucial exception: it is the responsibility of the investigator to keep a 'Subject Identification Log' up to date, where personal identification information matches the Subject ID (see below). The 'Subject Identification Log' must be kept up to date and stored in the Investigator Site File (ISF) in a secure location with restricted access. This log will not, at any time during and after the investigation, be available to any unauthorised party, nor available in the sponsor files.

All subjects enrolled in the investigation will be provided with a Subject Identification Number (i.e. pseudonymization), consisting of a three digit code, where the leading digit represents the investigation site number, (e.g. 100 for site no. 1, 200 for site no. 2 etc.) and the two following numbers represents the consecutive subject number (e.g. 101 for the first enrolled subject at site no. 1, 202 for the second enrolled subject at site no. 2 etc.). In case of bilateral surgery, the two sides will result in two different entries in the electronic data capture (EDC) system, one for each implant/abutment complex (e.g. 101L and 101R).

